5.3 Justification of Clinical Investigation Design

This is a prospective, multi-center study intended to evaluate the safety of SJM MR Conditional ICD system in an MRI environment with 1.5 Tesla and 3.0 Tesla scanning machines by demonstrating the superiority of freedom of MRI-scan related complications for ICD system from MRI scan to 1 month post MRI scan against the performance goal of 90%. The time point for evaluation the endpoint is designed to capture MRI scan related complications related to ICD system which are most likely occurred within one month of scan.

5.4 Multiplicity Adjustment

The primary endpoint will be evaluated for each phase separately at 2.5% significance level. Therefore, no multiplicity adjustment is planned for this study.

Clinical Investigation Plan

5.5 Overall Sample Size

Minimum 396 subjects (198 in each phase) will be enrolled in this study in order to meet the minimum target requirement for primary endpoint for each phase.

5.6 Timing of Analysis

The analysis will be conducted for each phase separately. The dataset will be frozen for analysis for each phase when 168 subjects have completed the 1 month post MRI scan visit.

Success Criteria

Success will be assessed for SJM MR Conditional ICD system in an MRI environment for each phase separately, i.e. safety of SJM MR Conditional ICD system will be established if the primary endpoint is met for each phase, respectively.

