3.1 Clinical Investigation Design

This clinical investigation is a prospective, multicenter, 2-phase, single arm, Asian study.

- In the 1st phase patients will be enrolled at least 60 days post successful implant with a St. Jude Medical™ MR Conditional ICD System approved for thoracic scan with 1.5 Tesla MRI scanning machines.
- In the 2nd phase patients will be enrolled at least 60 days post successful implant with a St. Jude Medical™ MR Conditional ICD System approved* for thoracic scan with 3.0 Tesla MRI scanning machines.

*NOTE: The 2nd phase of this study will start only after receiving appropriate regulatory approval for MRI labelling at 3.0T and phase 1 enrollment has completed. The Sponsor will notify each ethics committee and site when Phase 2 may begin. Patient can be enrolled only in one of the two phases of the study.

A prospective, multi-center study design was chosen for generalizability of study results by enrolling subjects across multiple geographies and sites, with the minimum sample size required to demonstrate the safety of St. Jude Medical™ MR Conditional ICD System in an MRI environment with 1.5 Tesla and 3.0 Tesla scanning machines.

Enrollment of the study is expected to require 36 months. The anticipated duration of the study is 42 months, depending on the rate of enrollment and regulatory timelines (CE approval of St. Jude Medical™ MR Conditional ICD System for thoracic scan with 3.0 Tesla MRI scanning machines for 2nd Phase and phase 1 enrollment has completed).

The clinical investigation will enroll at least 396 subjects (198 in each phase) up to 40 centers across Asian Countries.

Subjects will be enrolled, undergo the study MRI scans, and followed for one month following the study MRI scan. The minimum duration of each subject's participation is approximately one month from the MRI scan (1 Month Post Scan visit).

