4.2 Study Procedures

This clinical investigation will be conducted in accordance with this clinical investigation plan (CIP). All parties involved in the conduct of the clinical investigation will be qualified by education, training, or experience to perform their tasks and this training will be documented appropriately.

The clinical investigation will not commence until Sponsor receives written approval from the IRB/EC and relevant regulatory authorities (if applicable) and all required documents have been collected from the investigational site(s).

Subjects who are pectorally implanted with a St. Jude Medical™ MR Conditional ICD System at least 60 days will be enrolled. Enrolled subjects will undergo an elective MRI scan within 30 days post enrollment. Post MRI visit all subjects will be followed up at 1-Month post MRI visit.

The following sections provide a detailed description of procedures required by this Clinical Investigation Plan.

Table-1 Specific Study Procedures & Data Collection

Study Visit	Visit Window	Study Procedures & Data Collection	Forms and CRFs
Enrollment		
• Screen subject for enrollment eligibility• Obtain informed consent(s)• Complete MRI Screening Form• Obtain medical and surgical history• Collect demographic information• Document indication for implant of ICD• Obtain ICD system information: model and serial number of implanted St. Jude Medical™ MR Conditional ICD System, and if applicable, most recent lead revision information.• Evaluate subject Adverse Device Effect (ADE) and Serious Adverse Device Effect (SADE), and submit an AE CRF (as applicable).	
• Signed and Dated Patient Informed Consent Form(s)• MRI Screening Form• Enrollment CRF

Clinical Investigation Plan

Study Visit	Visit Window	Study Procedures & Data Collection	Forms and CRFs

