One Month Post- MRI Scan Visit	30 days post MRI scan (- 7/+14 days)	
• Interrogate device• Obtain in-clinic lead measurements: ventricular bipolar capture threshold, ventricular sensing amplitude, ventricular pacing impedance and high voltage lead impedance*#• Evaluate subject Adverse Device Effect (ADE) and Serious Adverse Device Effect (SADE), and submit an AE CRF (as applicable).• Report deviations, death, withdrawal and out of service as applicable• Upload device session record (X-file) through the EDC study site portal	
• Follow Up CRF• Device session records (X-Files) 
If applicable:
 
• AE CRF• Deviation CRF• Death CRF• Withdrawal CRF• Product Out of Service CRF
Unscheduled (if applicable)	Any time after Enrollment visit (where the subject is seen in clinic due to an ADE, SADE)	
• Interrogate device• Obtain in-clinic lead measurements: ventricular bipolar capture threshold, ventricular sensing amplitude, ventricular	
• Follow Up CRF• Device session records (X-Files)• AE CRF

Clinical Investigation Plan

Study Visit	Visit Window	Study Procedures & Data Collection	Forms and CRFs
		
pacing impedance and high voltage lead impedance*#
 
• Evaluate subject Adverse Device Effect (ADE) and Serious Adverse Device Effect (SADE), and submit an AE CRF (as applicable).• Report deviations, death, withdrawal and out of service as applicable• Upload device session record (X-file) through the EDC study site portal	
If applicable:
 
• Deviation CRF• Death CRF• Withdrawal CRF• Product Out of Service CRF

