5.1.1.3 Analysis Populations

The analysis will be conducted on subjects who meet all of the following criteria:

- Implanted with the SJM MR Conditional ICD system
- Sign informed consent
- Meet the MRI Conditions of Use
- Undergo a MRI scan
- Have 1 month post MRI scan visit or have MRI-scan related complication(s) related to SJM MR Conditional ICD system before the 1 month post MRI scan visit

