5.2 Descriptive Endpoints

- Demographics and medical/surgical history such as gender, age, history of smoking, cardiac disease history, arrhythmia history, and indication for ICD implant, etc. Continuous variables will be summarized as sample size, mean, standard deviation, minimum and maximum. For categorical variables, the counts and percentages of subjects will be summarized for each category.
- Proportion of SJM high voltage lead implanted with SJM MR Conditional ICD with capture threshold increase of $\leq 0.5V$ @ 0.5ms from pre-MRI scan testing to 1 month post-MRI scan testing.
This proportion will be calculated as number of subjects who had high voltage lead with

[REDACTED]

Clinical Investigation Plan

capture threshold increased of $\leq 0.5V$ @ 0.5ms from pre-MRI scan testing to 1 month post-MRI scan testing divided by total number of subjects who had high voltage lead implanted, undergo a MRI scan and with both pre-MRI scan and 1 months Post MRI scan capture threshold available.

- Proportion of SJM high voltage lead implanted with SJM MR Conditional ICD with sensing amplitude decrease of $\leq 50\%$ from pre-MRI scan testing to 1 month post-MRI scan testing. This proportion will be calculated as number of subjects who had high voltage lead with sensing amplitude decrease of $\leq 50\%$ from pre-MRI scan testing to 1 month post-MRI scan testing divided by total number of subjects who had high voltage lead implanted, undergo a MRI scan and with both pre-MRI scan and 1 months Post MRI scan sensing amplitude available.
- Average and Peak Specific Absorption Rate (SAR) during MRI scan, MRI visit duration in MRI laboratory and total MRI scan duration in MRI laboratory
Average and Peak Specific Absorption Rate (SAR) during MRI scan, MRI visit duration in MRI laboratory and total MRI scan duration in MRI laboratory will be summarized as mean, standard deviation, minimum, median and maximum.
- Adverse events and death
The number of events, number of subjects who encountered the events will be summarized for each event category for ADE and SADE separately. The number of death will be summarized as counts and percentages for each primary cause.

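### Section 5.6 freezes each phase at the 168th completed visit of at least 198 enrolled: if loss is below about 15%, pending subjects count only as failures (small, conservative effect)

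*Combined protocol and SAP*

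**What the plan says.** Section 5.6 (Timing of Analysis) sets the data cut by a count of visits: "The dataset will be frozen for analysis for each phase when 168 subjects have completed the 1 month post MRI scan visit". Section 5.5 sets the enrolment: "Minimum 396 subjects (198 in each phase) will be enrolled in this study".

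Section 5.1.1.3 decides who is analysed. Besides implant, consent, conditions of use and a scan, a subject must satisfy an either/or condition ("Have 1 month post MRI scan visit or have MRI-scan related complication(s"), where the complication must come before the 1-month visit. Section 5.1.1.5 plans no imputation, and section 5.7 plans no interim analysis.

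The calendar is in section 4.2: "Enrolled subjects will undergo an elective MRI scan within 30 days post enrollment". The final visit is due 30 days after the scan, with a window of 7 days before to 14 days after. Section 3.1 adds the pace: "Enrollment of the study is expected to require 36 months", for both phases together.

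The test in section 5.1.1 is one-sided at 2.5%. A phase passes if the exact Clopper-Pearson 97.5% lower bound for freedom from complications exceeds 90%. Section 5.1.1.2 (Sample Size Determination) is redacted.

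**The concern.** The number 168 looks like the evaluable target after an allowance for loss, but section 5.6 uses it as the trigger for the freeze. If fewer subjects are lost than allowed for, the 168th completer arrives before the enrolled cohort has finished.

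The either/or condition in section 5.1.1.3 is sensible once everyone has finished. At a cut in mid-cohort it works differently. A scanned subject still waiting for the visit is in the analysis if a complication has already occurred and out if it has not, so inclusion depends on outcome. Subjects not yet scanned are out whatever happens later. The readable text describes no later update of the primary analysis. At stake is whether the one confirmatory test per phase uses the cohort that was enrolled for it.

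**Working it through.** **1. The plan's own figure.** 168/(1 − 0.15) = 197.6, which rounds up to 198. The break-even loss is 1 − 168/198 = 15.15%. The 15% is inferred.

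**2. Completers after the freeze.** 198 × (1 − loss) − 168:

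| Loss | Completers of 198 | After the freeze |
|---|---|---|
| 15% | 168 | about 0 |
| 10% | 178 | about 10 |
| 5% | 188 | about 20 |
| 0% | 198 | 30 |

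**3. Subjects pending at the freeze.** Pace: 396/36 = 11 per month, assuming even enrolment and no gap between phases. Scanned and awaiting a 30-day visit: 11 × 30/30.4 = 10.9. The window edges give 11 × 23/30.4 = 8.3 and 11 × 44/30.4 = 15.9. I use 11.

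**4. Pass limit.** The largest number of events m(n) that keeps the exact lower bound above 90% is 9 for n = 167–179, 10 for n = 180–192 and 11 for n = 193–199. For example, 9/168 gives 90.07% (pass), 10/168 gives 89.33% (fail) and 10/180 gives 90.02% (pass).

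**5. Operating characteristics.** Let q = 1 − true freedom, k = pending subjects and f = share of pending events known at the freeze. Then

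- P(pass at freeze) = Σₑ Bin(e; k, f·q) × P(X ≤ m(168+e) − e), with X ~ Bin(168, q);
- P(pass, all completers) = P(X ≤ m(n)), with X ~ Bin(n, q);
- bias at f = 1 is Σₑ Bin(e; k, q) × 168(1−q)/(168+e) − (1−q).

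These treat complications as independent of loss and of timing.

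*Type I error* at true freedom 90%, k = 11: 2.33, 1.72 and 1.25% for f = 0, ½ and 1.

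*Bias and power.* The planning value is redacted, so a range of true freedom is shown:

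| True freedom | 95% | 96% | 97% | 98% |
|---|---|---|---|---|
| Bias in points, k = 11, f = 1 | −0.31 | −0.25 | −0.19 | −0.13 |
| Power at freeze, k = 11, f = 1 | 59.4% | 81.8% | 95.5% | 99.7% |
| Power at freeze, k = 11, f = ½ | 63.1% | 84.1% | 96.3% | 99.7% |
| All completers, 10% loss (n = 178) | 60.1% | 82.2% | 95.7% | 99.7% |
| All completers, 5% loss (n = 188) | 66.0% | 86.5% | 97.3% | 99.8% |
| All completers, 0% loss (n = 198) | 71.1% | 89.8% | 98.3% | 99.9% |

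With 16 pending and f = 1, power at the freeze is 56.0/79.6/94.8/99.6%. The exact test is saw-toothed: 168 subjects alone give 66.8% at 95% freedom, more than 178 do, because both allow 9 events.

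**6. Can the verdict change?** Yes, near the limit and in both directions.

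- 9/168 passes at the freeze. One later complication among 10 pending makes 10/178, with bound 89.91%, which fails.
- Nine events among 168 completers plus one known pending event make 10/169, with bound 89.39%, which fails. If 188 finish with no further event, 10/188 gives 90.44% and passes.

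With k = 11, f = ½, 5% loss and 95% freedom, summing over events in the 168, in the 11 pending and in the 9 not yet scanned gives 5.6% for fail at the freeze but pass on the full cohort, and 2.7% for the reverse. At 98% freedom both are 0.2% or less.

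**The case against.** **The redaction.** Section 5.1.1.2 is where a loss allowance and the handling of surplus subjects would normally stand. A gap caused by redaction is not a gap in the plan. This stands as a caveat: the point concerns the readable wording of 5.6 read with 5.1.1.3.

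**Loss below 15% is assumed.** The protocol withdraws subjects before the scan for several reasons, such as some system revisions, pregnancy or a need for pacing support. They count toward 198 and never toward 168. At the inferred allowance nobody is left out. This stands too, so the concern is conditional.

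**Section 5.6 fixes timing and does not cap the analysis at 168.** That is right. The omission of later completers is inferred from the freeze together with the lack of any described update.

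**Stronger readings that a reader might infer, and why they fail.**

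- *That the freeze inflates false-positive risk.* It does not. The trigger counts visits, not outcomes, and pending subjects can add only failures.
- *That a phase cannot be analysed if loss exceeds 15%.* Section 5.5 makes 198 a minimum, so enrolment may continue until 168 complete.
- *That later complications go unseen.* Section 8.2 continues safety reporting to the last visit, and section 5.2 plans that the "number of subjects who encountered the events will be summarized for each event category for ADE and SADE separately". Those events are reported, but they are not part of the test.
- *That waiting always gains power.* At about 10% loss it does not.

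**The freeze count is independent of outcome, whereas an open-ended close of enrolment would leave the final n to the sponsor.** In an unblinded single-arm study this is a fair warning about any repair, and the fix below fixes the enrolment number in advance.

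**Conclusion.** The point holds, as a minor one. If loss is below about 15%, sections 5.6 and 5.1.1.3 together select pending subjects by outcome and leave later completers out of the only primary test for the phase.

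The error in the estimate runs against the device, and type I error does not rise above 2.33%. A positive result is therefore not undermined in the long-run sense, although a single phase near 9 to 10 events could change verdict either way. The power cost against analysing all completers at 95% freedom, with all pending events known, runs from 0.7 points at 10% loss (60.1 − 59.4) to 11.7 points at 0% loss (71.1 − 59.4). At 98% it is at most about 0.3 points.

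These sizes rest on four assumptions that the documents do not settle: the inferred 15% allowance, 11 enrolled per month, the share of pending events known at the freeze, and a true freedom of 95 to 98%. This is a cheap improvement to the plan, not a threat to its validity.

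**What to change.** Replace the freeze sentence in section 5.6 with:

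> Enrolment in each phase closes at 198 subjects, or at a higher maximum fixed in advance without reference to outcomes. The dataset for the phase is frozen when every enrolled subject has completed the 1-month visit, exited the study, or passed the end of the visit window. All subjects meeting 5.1.1.3 are analysed once; at least 168 are expected, and any shortfall is reported.

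If the redacted section already covers surplus subjects, 5.6 should be made to agree with it.

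The cost is three sentences and a wait of at most about 74 days after the last enrolment if windows are kept: 30 days to the scan, then 30 + 14 = 44 days to the end of the visit window. No patients beyond the stated minimum are needed. Phase 2 is not held up, because under section 3.1 it "will start only after receiving appropriate regulatory approval for MRI labelling at 3.0T and phase 1 enrollment has completed"; its start does not depend on the Phase 1 analysis. At about 10% loss the change brings no real gain in power. What it brings is an analysed cohort that does not depend on outcome.

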5.7 Interim Analysis

There are no interim analyses planned for this study.

5.8 Statistical Criteria for Termination

There are no statistical criteria for termination of this study.

5.9 Deviations from Statistical Plan

If any deviations from the original statistical plan occur, such deviations will be documented in the clinical study report or statistical report containing the analysis results.

6 Device(s) under investigation

The following market-released devices* will be used in this clinical investigation in an MRI environment according to MRI-conditional labeling.

Table- 4: Identification of Devices* under Investigation

Device name	Model/Type/Description	Manufacturer	Region/ Country	Investigational or Market Released
Ellipse VR	CD1377-36QC/ICD/Single Chamber	SJM	Outside US	Market Released
Ellipse VR	CD1377-36Q/ICD/Single Chamber	SJM	Outside US	Market Released
Ellipse DR	CD2377-36QC//ICD/Dual Chamber	SJM	Outside US	Market Released
Ellipse DR	CD2377-36Q/ICD/Dual Chamber	SJM	Outside US	Market Released
Durata	7120Q/Lead/Active fixation, dual shock, 17 cm spacing, DF4	SJM	Outside US	Market Released

**Clinical Investigation Plan**

	connector, 58/65cm length			
Durata	7122Q/Lead/Active fixation, single shock, DF4 connector, 58/65 cm length	SJM	Outside US	Market Released
Optisure	LDA220Q/Lead/Active fixation, dual shock, 17 cm spacing, DF4 connector, 58/65cm length	SJM	Outside US	Market Released
Optisure	LDA210Q/Lead/Active fixation, single shock, DF4 connector, 58/65 cm length	SJM	Outside US	Market Released
Tendril MRI	LPA 1200M/Lead/ Active fixation, Bipolar, Pacing 46/52/58cm length	SJM	Outside US	Market Released

*Apart from the devices listed in Table 4; any other CE-marked St. Jude Medical MRI compatible ICD system market released in participating countries approved for Thoracic MRI scan with 1.5 Tesla (1st Phase of enrollment) & 3.0 Tesla (2nd Phase of enrollment) scanning machines can be used for this clinical investigation.

6.1 Device Description and Intended purpose

6.1.1 Ellipse ICD

The Ellipse ICD is supported by the St. Jude Medical Merlin Patient Care System (Merlin PCS) with software Model 3650, Software Model 3330 version 20.X (or higher). The Ellipse ICD is intended to provide ventricular antitachycardia pacing and ventricular defibrillation for automated treatment of life-threatening ventricular arrhythmias.

Instructions for use, storage and handling instructions, preparation for use and any precautions can be found in the User's Manual for the Ellipse ICD.

6.1.2 Durata Lead

The Durata Models 7120Q, and 7122Q leads are market-released 7 French, transvenous, steroid eluting, bipolar, DF4 compatible (single connector with four electrical terminals), active fixation leads intended for permanent sensing and pacing of the right ventricle and the delivery of cardioversion/defibrillation therapy when used with a compatible St. Jude Medical pulse generator with a DF4-LLHH or DF4-LLHO lead receptacle designation.

Instructions for use, storage and handling instructions, preparation for use and any precautions can be found in the User's Manual for the Durata lead.

6.1.3 Optisure Lead

The Optisure Models LDA220Q and LDA210Q transvenous leads are market-released leads indicated for use with compatible pulse generators (refer to the applicable defibrillator manual for system indications). They provide pacing and sensing and deliver cardioversion/defibrillation therapy to the heart.

**Clinical Investigation Plan**

Instructions for use, storage and handling instructions, preparation for use and any precautions can be found in the User's Manual for the Optisure Lead.

6.1.4 Tendril MRI Lead

The Tendril MRI Lead Models LPA 1200M 46/52/58cm length transvenous leads are market-released leads indicated for use with compatible pulse generators (refer to the applicable manual for system indications). They provide pacing and sensing to the heart.

Instructions for use, storage and handling instructions, preparation for use and any precautions can be found in the User's Manual for the Tendril MRI Lead.

6.2 Device Handling & Storage

This study involves use of market approved products. Physicians should consult the User's manual for device handling and storage.

7 Risks and Benefits of the clinical study**7.1 Anticipated Adverse Device Effects**

The below list of anticipated adverse device effects represents the summary of the most common events observed and documented in literature associated with the patient medical condition and associated with the medical device exposure.

The St. Jude Medical™ MR Conditional ICD System are market-released devices. Risks associated with the use St. Jude Medical™ MR Conditional ICD System are anticipated to be comparable to those associated with the use of other market-released defibrillation leads, pacing leads, and ICDs. Subjects participating in this study are indicated for or implanted with an ICD as part of their standard medical management and are subject to the risks associated with these devices independent of the subject's participation in the study.

The St. Jude Medical™ MR Conditional ICD System are being tested in an MRI environment, and subjects participating in the study are required to undergo the study MRI scans which are investigational for the purposes of investigating the effect the scan has on the implanted ICD system. The subjects are therefore exposed to, but not limited to, an incremental risk of experiencing the events listed below.

Clinical Investigation Plan

Table-5: Anticipated Events and Anticipated Adverse Device Effects

Event	Mitigation
Potential MRI Related Events 
• Lead electrode heating and tissue damage resulting in loss of sensing or capture or both• Lead heating resulting in thrombus formation or embolism• Device heating resulting in tissue damage in the implant pocket or subject discomfort or both• Induced currents on leads resulting in continuous capture, VT/VF, hemodynamic collapse, or all three• Damage to the device or leads causing:
a. the system to fail to detect or treat irregular heartbeatsb. the system to treat the subject's condition incorrectly• Damage to the functionality or mechanical integrity of the device resulting in the inability of the device to communicate with the programmer• Movement or vibration of the device or leads• Lead dislodgment• Competitive pacing and potential for VT/VF induction due to ambulatory asynchronous pacing in MRI mode• Pulmonary Embolism	
These risks are mitigated through the selection of investigators who are qualified by training and/or experience to evaluate and treat subjects implanted with an ICD system.
 
In addition, study investigators will be trained on the study protocol to ensure the proper procedures are followed to assure subject safety during the study MRI scan. This includes continuous monitoring of the subject using pulse oximetry, ECG and verbal communication during the scan.
 
Advanced Cardiac Life Support (ACLS) procedures will be in place to address situations where a life threatening arrhythmia and/or hemodynamic collapse occurs. The programmer will be used outside the American College of Radiology (ACR) defined Zone 4 magnet room. If the subject's hemodynamic function is compromised during the MRI scan, the MRI scan will be stopped, and proper measures will be taken to restore the subject's hemodynamic function.

Potential ICD Related Events 
• Refer to the Device user's manual for a full list of potential adverse events (Refer to Appendix-I)	The ICD which will be used in this investigation are a market-released ICD. The adverse events associated with this ICD are

Clinical Investigation Plan

Event	Mitigation
	
the same as those associated with other market-released ICDs.
 
These risks are mitigated through the selection of investigators who are qualified by training and/or experience to evaluate and treat subjects implanted with an ICD.

Potential Lead Related Events	
Refer to the lead user's manual for a full list of potential adverse events (Refer to Appendix-I) 
The high voltage leads are market released transvenous, steroid-eluting defibrillation leads. The adverse events associated with these leads are the same as those associated with other market-released transvenous defibrillation leads.
 
These risks are mitigated through the selection of investigators who are qualified by training and/or experience to evaluate and treat subjects implanted with an ICD system.

In addition, subjects may also experience unavoidable events related to the MRI scan. An unavoidable event is an event related to the MRI scan that is expected to occur for a projected duration in all subjects. Unavoidable events are not reportable unless the condition worsens or continues beyond the time frame listed below. Unavoidable events do not need to be reported on an adverse event form if they are resolved within the time frame specified. These events are expected to occur with any MRI scan, including the study MRI scans.

Clinical Investigation Plan

Table 6: Unavoidable events related to the MRI Scan

Event	Time Frame post – MRI scan
• Claustrophobia	• During MRI scan
• Mild diaphoresis	• During and < 1 hour post MRI scan
• Sensation of bodily warmth	• During and < 1 hour post MRI scan
• Sensation of warmth at device pocket not arising to the level of discomfort	• During and < 1 hour post MRI scan
• Hearing impairment	• < 24 hours
• Body stiffness related to immobility	• < 48 hours

